A comparative study of Vitamin D serum levels in monosymptomatic enuretic children and non-enuretic children

INTRODUCTION

Nocturnal enuresis is a widely prevalent problem. It occurs in up to 15% of 5-year-old children and 10% of 10-year-old, with a spontaneous remission rate of 14% per year. Bedwetting can have a considerably distressing social impact on children and subsequently their families, affecting children's self-esteem and interpersonal relationships, and their scholastic achievement.¹

Nocturnal enuresis is classified into monosymptomatic (MNE) and non-monosymptomatic (NMNE), depending on whether it is associated with voiding or storage symptoms or not. It can also be categorized into primary, which is since birth, and secondary enuresis, which is newly onset after at least 6 months of a previous asymptomatic state.²

Primary monosymptomatic nocturnal enuresis (PMNE) is the most frequent urologic complaint among pediatric patients; however, the pathology and etiology of this problem have not been clearly determined.³

Nocturnal bladder control is a matter of developmental delay. At 1 year of age, the conscious sensation of urinary bladder fullness starts to evolve and this physiological turning point allows the beginning of the development of voluntary control of voiding by the age of 2 years.⁴ By the age of 4 years, full daytime and nighttime urinary control is obtained by most children.⁵

The idea that enuresis is related to the immaturity of the central nervous system is supported by the finding that premature and/or low-birth-weight children experienced bed-wetting more often than normal-birth-weight children.⁶

Low nocturnal anti diuretic hormone (ADH) and urine osmolality play a role in MNE associated with Nocturnal Polyuria (NP), which doesn't occur as an isolated abnormality but is also linked to children who also suffer of arousal abnormality⁷. We have proved this in our previous study in which we stated that Nocturnal polyuria and decreased nocturnal urine osmolality were key factors in pathogenesis of nocturnal enuresis⁷.

There are many clinical observations that link nocturnal enuresis with developmental delay in language and physical growth⁸ and skeletal maturation.⁹ Nocturnal enuresis could be linked with sleep disorders as well.¹⁰

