Vitamin D is important for bone growth and regulation of calcium homeostasis. It not only plays a vital role in skeletal growth but also has other critical biological actions in neural development and function.¹¹

The source of vitamin D is primarily sunlight; it is also found in few foods as oily fish and fortified margarine. Vitamin D consists of a cholesterol backbone and has steroid-like effects. It is the fat-soluble hormone that plays an essential role in brain health.¹²

Studies claim that vitamin D may have an essential role in sleep regulation¹³.

Vitamin D deficiency is linked with Obstructive Sleep Apnea (OSA)¹⁴ and nocturnal polyuria is one of the main adverse outcomes of OSA.¹⁵

Vitamin D deficiency could cause excessive urine production directly. This was shown in a study done on mice which showed that vitamin D deficiency leads to activation of the Renin Angiotensin system. Eventually the augmentation of renin synthesis leads to increased

plasma Ang II production from angiotensinogen, which drives mice to increase water intake and intestinal salt absorption, since Ang II is a very potent thirst-inducing agent that acts on the central nervous system, as well as a potent stimulator of intestinal sodium absorption. As a result, the mice must excrete more urine and salt to maintain volume and electrolyte homeostasis.⁽¹⁶⁾

AIM OF THE STUDY

To evaluate the relationship between Vitamin D deficiency and nocturnal enuresis, and to study the correlation between vitamin D deficiency and urine osmolality which is an indirect indicator of ADH deficiency.

PATIENTS AND METHODS

This is a case control study which was performed in Ain Shams University Hospitals. It was conducted in the period between February 2021 and August 2021.

Patient group: Sixty children aged from 5 to 15 with primary mono-symptomatic nocturnal enuresis were included and selected randomly.

Inclusion criteria: Patients with PMNE which was defined as bedwetting frequency of 3 or more nights per week for at least 2 weeks of observation, and who didn't receive any previous treatment for enuresis.

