Exclusion criteria: Patients with non-monosymptomatic enuresis (associated with storage and/or voiding symptoms), anatomical abnormalities (Meatal stenosis, Hypospadias, Epispadias, etc.), neurological diseases, renal impairment, previous pelvic, urological or brain and spinal cord surgery, chronic constipation and irritable bowel habits, active urinary tract infection and patients who are on vitamin D supplements.

Control group: Sixty healthy children were included as a control group whose ages ranged from 5 to 15 years old, and they were chosen from apparently healthy non-enuretic children.

Written informed consent was obtained from patients' legal guardians, and the study was approved by Ain Shams University Ethical Committee.

Methods:

All children included in the study were subject for detailed medical and surgical history to rule out the presence of organic or psychological diseases. Physical examination including focused neurological examination to exclude neurological diseases, especially (neural tube defects) and local urological examination to check for any genital or external urethral meatus anomalies. Also urine analysis was done to exclude urinary tract infection.

Frequency Volume chart and nocturnal urine osmolality.

Volume Frequency chart was recorded for both enuretic and control groups, to evaluate frequency, average voided volume, and to exclude or confirm the presence of nocturnal polyuria.

Nocturnal polyuria is defined in children and adolescent age group as, urine production during the period of sleep which equals to or more than 130% of estimated bladder volume for age (EBV).⁽¹⁷⁾

Estimated bladder capacity for age is calculated by the formula [30 X (age in years + 2)] in ml. The amount of urine last voided before sleep is discarded and first morning voiding volume is

added to the calculated nocturnal urine volume. Clear instructions for mothers were to let the child void before sleep and every two hours till 8 am. Short intervals were meant to avoid enuretic episodes during calculation of nocturnal urine volume, and if occurred it mandates the repeat of chart on another day.

Nocturnal urine collected over the night was tested for osmolality, it was measured in mOsm/kg.

Serum Vitamin D level.

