Vitamin D serum level was measures using the ELISA technique. The Cal Biotech Vitamin D Kit (Mannheim, Germany) was used, which is a solid phase enzyme linked immunoassay (ELISA), based on the principal of competitive binding. Vitamin D deficiency was defined as serum Vit. D below 20 ng/ml.

Sensitivity:

The sensitivity of this test kit is 0.67ng/ml. Sensitivity was determined by calculating the mean plus 2SD of the standard zero point tested 20 times in the same Statistical Methods run.

Statistical methods

The collected data were coded, tabulated, and statistically analyzed using IBM SPSS statistics (Statistical Package for Social Sciences) software version 28.0, IBM Corp., Chicago, USA, 2021. Quantitative data tested for normality using Shapiro-Wilk test, then described as mean \pm SD (standard deviation), and then compared using independent t-test. Qualitative data described as number and percentage and compared using Chi square test. Pearson test was used for correlations. ROC curve was used to evaluate the performance of variables to differentiate between conditions. The level of significance was taken at p-value <0.050 was significant, otherwise was non-significant.

Diagnostic characteristics was calculated as follows:

- Sensitivity = (True positive test / Total positive golden) x 100
- Specificity = (True negative test / Total negative golden) x 100
- Diagnostic accuracy = ([True positive test + True negative test] / Total cases) x 100
- Youden's index = sensitivity + specificity - 1
- Predictive positive value = (True positive test / Total positive test) x 100
- Predictive negative value = (True negative test / Total negative test) x 100
- Likelihood ratio positive (LR+) = (sensitivity / 1-specificity)
- Likelihood ratio negative (LR-) = (1- sensitivity / specificity)

Diagnostic odds ratio (DOR)= LR+/ LR-

Serum level of vitamin D, in monosymptomatic enuretic children and non-enuretic children: a comparative study

[name] [name]*, [name]. [name]*, [name] **, [name]*.

* Urology Department, Faculty of Medicine, Ain Shams University

** Damanhour National Medical Institute.

Corresponding Author:

[name] [name]

Associate professor of urology

Faculty of Medicine

Ain shams university

Email: [contact]

[contact]

[name], Faculty of medicine, El Demerdash hospital.

[name]

[contact]

Professor and chief of urology department

Faculty of medicine

Ain Shams university

[name]

[contact]

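### Does the unstated analysis set for the vitamin D and osmolality correlation leave the second aim without a usable analysis?

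*Combined protocol and SAP*

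**What the plan says.** The Aim of the Study has two parts: the relation of vitamin D deficiency to enuresis, and "to study the correlation between vitamin D deficiency and urine osmolality which is an indirect indicator of ADH deficiency". The text in Statistical methods that addresses correlations is one sentence: "Pearson test was used for correlations". It names no variables, no group and no adjustment.

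The design is case-control, with 60 enuretic children, and "Sixty healthy children were included as a control group". Under the heading on the frequency volume chart and nocturnal urine osmolality, "Volume Frequency chart was recorded for both enuretic and control groups", but the sentence on osmolality names no group. Deficiency is a serum level below 20 ng/ml; the level itself is also measured.

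The Introduction gives reasons to expect both variables to be related to enuresis. From the authors' earlier work: "Nocturnal polyuria and decreased nocturnal urine osmolality were key factors in pathogenesis of nocturnal enuresis". On vitamin D: "Vitamin D deficiency could cause excessive urine production directly", and, less firmly, "Studies claim that vitamin D may have an essential role in sleep regulation". It also gives the frequency of enuresis in children: "It occurs in up to 15% of 5-year-old children and 10% of 10-year-old".

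**The concern.** Cases make up half of this sample but about 10% to 15% of children by the Introduction's figures. If both variables differ between cases and controls, pooling the 120 children adds the gap between the two group means to the correlation. If both variables influence enuresis, restricting to cases or adjusting for group conditions on a common effect, which can pull the coefficient down. The same data could then give a positive pooled coefficient and a negative one in cases. A reader told only that a Pearson correlation was computed could not say which relation it describes, and might read it as support for a mechanism through antidiuretic hormone.

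**Working it through.** The plan states no correlation, power or effect size, so there is no figure of its own to reproduce. The inputs from the documents are 60 cases, 60 controls, the 0.05 level (taken as two-sided) and the 10% to 15% prevalence. All group differences, slopes and correlations below are assumptions.

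**1. Pooled against within-group.** Let r_w be a common within-group correlation, d_x and d_y the case-control differences in within-group SDs, p the case share and q = p(1-p). Then

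pooled r = (r_w + q·d_x·d_y) / √[(1 + q·d_x²)(1 + q·d_y²)].

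At 60:60, q = 0.25. With r_w = 0:
- d = 0.5 on both: 0.0625/1.0625 = 0.06
- d = 0.8 on both: 0.16/1.16 = 0.14
- d = 1.0 on both: 0.25/1.25 = 0.20

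The pooled test at 0.05 is then significant in about 9%, 33% and 60% of simulated studies. If only one variable differs (d_x = 1, d_y = 0), pooled r stays 0, and r_w = 0.30 becomes 0.30/√1.25 = 0.27. A material gap therefore needs sizeable differences on both variables.

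**2. Against children in general.** Model: bivariate normal variables, logistic risk of enuresis rising with low values of each, 10% prevalence, 1:1 sampling. Slopes are per SD, for vitamin D and osmolality in that order.

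| Population r | Slopes | Pooled | Cases | Controls |
|---|---|---|---|---|
| 0 | 0.5, 0.5 (d about 0.5) | +0.03 | -0.03 | -0.02 |
| 0 | 1.0, 1.0 (d about 0.87) | +0.08 | -0.13 | -0.06 |
| 0.30 | 0.5, 0.5 | 0.33 | 0.27 | 0.28 |
| 0.30 | 1.0, 1.0 (d about 1.1) | 0.38 | 0.14 | 0.24 |
| 0.30 | 0, 1.0 | 0.32 | 0.28 | 0.29 |
| 0.30 | 0.2, 1.0 | 0.33 | 0.26 | 0.28 |

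In the second row, p < 0.05 occurs in 14% of pooled analyses and 17% of cases-only analyses, so the usual result is two non-significant coefficients. The last two rows are the chain in which vitamin D acts wholly or mostly through urine output.

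**3. Dependence on the risk model.** If risk is proportional to exp(b_x·x + b_y·y), the distribution among cases is the population normal with its means moved and its covariance unchanged. The cases-only r then equals the population r. With slopes of 0.5, population r = 0 and prevalence 2% to 10%, simulation gives 0.00 in cases. This does not extend to strong effects at 10% prevalence: with slopes of 1.0, risk has to be capped at 1 and cases-only r is again about -0.13. A liability-threshold model with strong weights goes as far as -0.43. Both the presence and the size of the downward pull are modelling choices.

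**4. What a report would reveal.** Since t = r·√[(n-2)/(1-r²)], a coefficient and its p-value fix the sample size. For r = 0.30, n = 60 gives t = 2.40 and p = 0.020; n = 120 gives t = 3.42 and p = 0.0009. Pooled and single-group results can be told apart even without a label; only cases against controls needs one.

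**5. Form of vitamin D.** Pearson's coefficient is ordinarily applied to two measured quantities, which points to the serum level. Applied to the deficiency indicator, its test is the same as the equal-variance t-test of osmolality by deficiency status, which the section's general t-test sentence also covers. Either reading is a legitimate analysis.

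**The case for a change.** The strongest case for acting is that the omission is plain, is not redaction or damaged text, and concerns a stated aim. The Introduction ties both variables to case status. With strong effects the choice alters the conclusion: at population r = 0.30 and slopes of 1.0, p < 0.05 occurs in 99% of pooled analyses, 56% of group-adjusted ones and 20% of cases-only ones. Part of that spread is the use of 120 rather than 60 children, but the group-adjusted figure uses all 120. Stating the set costs one sentence.

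The omission stands, and so does the point that pooled and within-group coefficients answer different questions. The charge of bias does not stand in general. A coefficient is biased only against a named target, and the documents never claim to estimate the correlation among children in general; they study enuretic patients at one university's hospitals and selected healthy children. If cases are the target, the cases-only coefficient is free of this bias. Nor is the large-effect scenario the one the Introduction makes most natural: it places vitamin D upstream of urine output, and urine output upstream of enuresis. The sleep pathway allows a separate effect, but nothing suggests one as strong as that of osmolality. Weighting the sample back to an assumed prevalence would bring in a figure that the documents give only for nocturnal enuresis overall, for controls chosen because they are healthy. That is a trade-off, not a correction.

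**Conclusion.** The plan leaves out a detail; it does not prescribe a wrong analysis, and nothing says the groups were pooled. If osmolality was measured only in cases, just one analysis set is possible. If it was measured in both groups, showing the coefficient by group beside any pooled value is ordinary reporting practice and needs no change of method or data.

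The possible size is negligible at differences of about 0.5 SD (+0.03 against -0.03) and small if vitamin D acts mainly through urine output (0.32 against 0.28). It becomes material only from about 0.8 SD on both variables with separate effects on enuresis. All of this rests on assumed effects, since the documents supply none, and on the risk model chosen. Larger divergence is possible but cannot be inferred from the documents. Precision is limited in any case: an observed r of 0.30 has a 95% interval of 0.05 to 0.51 with 60 children and 0.13 to 0.45 with 120. The coefficient is descriptive on any reading and cannot establish mechanism. The comparison of vitamin D between groups is not affected. No change to the plan follows.

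### The aim 2 Pearson correlation spans ages 5 to 15 without adjustment, so any age trend shared by vitamin D and nocturnal osmolality would be mixed into r; an age-adjusted analysis costs almost nothing

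*Combined protocol and SAP*

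**What the plan says.** The second part of the Aim of the Study is "to study the correlation between vitamin D deficiency and urine osmolality which is an indirect indicator of ADH deficiency". In Statistical methods, the only sentence that can serve this aim is "Pearson test was used for correlations". The other methods listed are the Shapiro-Wilk test, the independent t-test, the chi-square test, ROC curves and diagnostic indices. None of them takes a covariate, and no partial correlation, regression or stratification is mentioned.

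Both groups cover a ten-year age span. For cases: "Sixty children aged from 5 to 15 with primary mono-symptomatic nocturnal enuresis were included and selected randomly". For controls: "Sixty healthy children were included as a control group whose ages ranged from 5 to 15 years old". No matching on age is described.

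Osmolality is measured in mOsm/kg with no reference to age. Nocturnal polyuria, by contrast, is judged against an estimated bladder capacity of 30 × (age + 2) ml.

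The plan leaves two further things open. It does not say whether the correlation is computed in cases only, in each group, or in all 120 children together. It also does not say whether Pearson uses the vitamin D level or the deficiency indicator (below 20 ng/ml).

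**The concern.** A two-variable correlation cannot separate a relationship between vitamin D and osmolality from a trend that each has with a third variable. Age is the obvious candidate in children of 5 to 15, and the Introduction itself frames the condition in terms of maturation: "Nocturnal bladder control is a matter of developmental delay".

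The Introduction also proposes a pathway from vitamin D deficiency to excess urine production, so a significant r under aim 2 will be read as support for that pathway. If vitamin D and osmolality move in the same direction with age, r can be significant with no age-independent link. If they move in opposite directions, r can turn negative, or a real positive link can be cancelled.

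Balancing cases and controls on age would not cure this, because the age trend lies inside the correlation and not between the groups.

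**Working it through.** The plan gives no sample-size calculation, expected correlation or power for this aim, so there is no figure of its own to reproduce.

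**Inputs from the documents.** 60 cases and 60 controls, aged 5 to 15 (Patients and Methods); significance at p < 0.050 (Statistical methods), taken as two-sided. Because the analysis set is not stated, both n = 60 and n = 120 are shown.

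**Assumed inputs.** a = correlation of vitamin D with age; b = correlation of osmolality with age; r_p = correlation of vitamin D with osmolality at fixed age. The documents give none of these. Age trends are taken as linear.

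**Formula.** Unadjusted r = r_p × √[(1 − a²)(1 − b²)] + a × b. Chance of significance by Fisher z: shift s = atanh(r) × √(n − 3), then P = 1 − Φ(1.96 − s) + Φ(−1.96 − s).

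**No age-independent link (r_p = 0), so r = a × b.**

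| a = b | r | n = 60 | n = 120 |
|---|---|---|---|
| 0.1 | 0.01 | 5.1% | 5.1% |
| 0.2 | 0.04 | 6.1% | 7.2% |
| 0.3 | 0.09 | 10.5% | 16.4% |
| 0.4 | 0.16 | 23.0% | 41.5% |
| 0.5 | 0.25 | 48.7% | 78.9% |

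Worked line for 0.4 at n = 120: atanh(0.16) = 0.1614; s = 0.1614 × √117 = 1.746; P = 1 − Φ(0.214) + Φ(−3.706) ≈ 0.415. Opposite signs of a and b give the same rates with negative r. One weak trend removes most of the effect: a = 0.1 with b = 0.3 gives r = 0.03 and about 6% at n = 120. If either is zero, age does not confound.

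**A real link (r_p = 0.30) with opposite age trends.**

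| a, b | r | power, n = 60 | power, n = 120 |
|---|---|---|---|
| 0, 0 | 0.30 | 64.7% | 91.7% |
| −0.2, 0.2 | 0.248 | 48.1% | 78.2% |
| −0.3, 0.3 | 0.183 | 28.7% | 51.7% |
| −0.4, 0.4 | 0.092 | 10.7% | 17.0% |
| −0.5, 0.5 | −0.025 | 5.4% | 5.8% |

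Worked line for −0.4, 0.4: 0.30 × 0.84 − 0.16 = 0.092.

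**Simulation check.** Age uniform on 5 to 15, r_p = 0, 20,000 studies per setting, a = b = 0.3, 0.4, 0.5. Unadjusted Pearson was significant in 10.5%, 23.2% and 49.1% of studies at n = 60, and in 16.2%, 41.9% and 79.8% at n = 120. The age-partial correlation stayed between 4.8% and 5.2% in all six settings.

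**Cost of adjusting for age.** Power for r_p = 0.30 with no age trend, replacing √(n − 3) by √(n − 4): 0.639 against 0.647 at n = 60, and 0.915 against 0.917 at n = 120.

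**Pooling cases and controls.** If the groups differ by d standard deviations in both variables, with no correlation within either group and equal group sizes, r = (d²/4) / (1 + d²/4). For d = 1 this is 0.25 / 1.25 = 0.20, significant in about 59% of studies at n = 120; for d = 0.5 it is 0.059, about 10%. Adjusting for age does not remove this when the groups are balanced on age.

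**The case against.** Confounding by age needs both variables to vary with age, and the documents report neither trend. The remark on developmental delay concerns continence, not urine concentration. The age-based formula scales a volume to bladder capacity; it does not show that a concentration needs an age allowance. For vitamin D the Introduction names sunlight and diet as sources and says nothing about age. All of this stands: age is a reasonable thing to allow for in this population, but not a demonstrated confounder here, and the larger figures above depend on values that nobody has documented.

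A reader might infer that the plan would declare a correlation where there is none. That goes too far. In the settings above the marginal correlation really is 0.04 to 0.25, and Pearson detects it correctly; aim 2 speaks of correlation and names no age-adjusted target. The result is false only if it is taken as an age-independent relationship. That reading is likely, given the proposed mechanism, but it is a matter of interpretation.

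A reader might also infer that age and sex are both available for every child. Age must be, because eligibility and the bladder-capacity formula need it. Sex is not named as a recorded variable.

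Finally, adjusting for age alone would be incomplete. If the groups are pooled, case status is the confounder with more support in the text: the Introduction ties low nocturnal osmolality to enuresis, and the first aim asks whether vitamin D deficiency is related to it. This objection is accepted and shapes the fix.

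**Conclusion.** The point holds in conditional form. Statistical methods offers only an unadjusted Pearson r for aim 2, in children spanning 5 to 15 years, so any age trend common to vitamin D and osmolality enters r and cannot be separated from the relationship that matters for the mechanism.

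Its size cannot be fixed from the documents. For spurious significance it is negligible when either trend is near zero or both are about 0.2, intermediate at 0.3, and material from about 0.4 on both variables. Masking appears somewhat sooner: opposite trends of 0.2 already take power for a true partial r of 0.30 from 91.7% to 78.2% at n = 120. These figures assume linear trends of equal strength; the n = 120 column also assumes pooling, which the plan does not state.

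This is a free improvement to the analysis. The documents do not support a claim that the planned correlation is wrong or that its result will be spurious.

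**What to change.** In Statistical methods, keep the Pearson r as a descriptive figure and base the aim 2 inference on one of two equivalent analyses: a partial correlation of vitamin D with nocturnal osmolality given age, or a linear regression of osmolality on vitamin D with age as a covariate. Use vitamin D as a continuous level in ng/ml. Add sex if it was recorded. Report the estimate with its 95% CI.

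State which children enter the analysis. If cases and controls are pooled, include a case/control term; otherwise report the analysis within each group.

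The cost is one degree of freedom for age and up to three with sex and group, a few lines of text and a standard SPSS procedure. No new data are needed if sex is treated as optional. Because Patients and Methods describes data collection as finished (February to August 2021), the adjusted analysis should be labelled as added later if it was not specified before the results were seen.

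### If enuresis status is the target, the planned PPV and NPV are values at a 50% prevalence that the 60:60 sampling created

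*Combined protocol and SAP*

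**What the plan says.** Under Patients and Methods: "This is a case control study which was performed in Ain Shams University Hospitals". On the patient group: "Sixty children aged from 5 to 15 with primary mono-symptomatic nocturnal enuresis were included". On the control group: "Sixty healthy children were included as a control group", chosen from children without enuresis. The case share is therefore 60 out of 120 by design.

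Cases are a selected group. They had "bedwetting frequency of 3 or more nights per week for at least 2 weeks of observation" and did not "receive any previous treatment for enuresis". Children with storage or voiding symptoms are excluded.

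Under Statistical methods, the list of diagnostic characteristics gives: "Predictive positive value = (True positive test / Total positive test) x 100". NPV is defined in the same way from the test-negative children, and accuracy as all correct results over all children. No definition contains a prevalence, and no sentence says that the results depend on the sampling ratio. The section names neither the index variable nor the target condition. It refers only to unspecified variables, conditions and a gold standard.

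The Introduction says of nocturnal enuresis: "It occurs in up to 15% of 5-year-old children and 10% of 10-year-old". The analysis section does not use these figures.

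**The concern.** A case-control table carries no information on how common the condition is, because the investigators set the proportion of cases. PPV and NPV depend on that proportion. Recruiting twice as many controls would lower the PPV with no change in the marker. With one control per case, the planned formulas act as though half of all children were enuretic.

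A PPV reported without a prevalence label can be read as the chance that a child with a positive marker is enuretic. Where fewer than half of children are enuretic, that reading overstates PPV and understates NPV; above 50% the direction reverses.

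**Working it through.** The plan gives no PPV, NPV, accuracy, sensitivity (Se) or specificity (Sp), so there is no figure to reproduce. The check is of the algebra, followed by an illustration.

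**Inputs.** From Patients and Methods: 60 cases and 60 controls. From the Introduction: prevalence p of up to 15% at age 5 and 10% at age 10. Assumed: enuresis status is the target, all 120 children enter the table, and the Se and Sp values below. A prevalence of 30% is also assumed, to represent a referral setting.

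**Step 1: what the plan's formulas return.** True positives = 60·Se and false positives = 60·(1-Sp), so

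PPV = 60·Se / [60·Se + 60·(1-Sp)] = Se / [Se + (1-Sp)].

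Bayes' rule gives PPV = Se·p / [Se·p + (1-Sp)(1-p)], which reduces to the same expression at p = 0.50. The same holds for NPV = Sp(1-p) / [Sp(1-p) + (1-Se)p]. The identity holds for any Se and Sp.

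**Step 2: size on the odds scale.** Odds of enuresis after a positive result = LR+ × p/(1-p). In the 60:60 table the prior odds are 1, so the inflation is (1-p)/p whatever Se and Sp are:

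- p = 0.15: 0.85/0.15 = 5.7
- p = 0.10: 0.90/0.10 = 9.0
- p = 0.30 (assumed): 0.70/0.30 = 2.3

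**Step 3: worked example, assumed Se = Sp = 80%.** The table is 48 true positives, 12 false negatives, 12 false positives and 48 true negatives. Raw PPV = 48/60 = 80% and raw NPV = 48/60 = 80%.

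- PPV at 15%: 0.12/(0.12 + 0.17) = 41%. At 10%: 0.08/(0.08 + 0.18) = 31%.
- NPV at 15%: 0.68/(0.68 + 0.03) = 96%. At 10%: 0.72/(0.72 + 0.02) = 97%.
- At the assumed 30%: PPV 63%, NPV 90%.

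**Step 4: range over assumed Se and Sp.**

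| Se / Sp | PPV: raw, at 15%, at 10% | NPV: raw, at 15%, at 10% |
|---|---|---|
| 70 / 70 | 70.0, 29.2, 20.6% | 70.0, 93.0, 95.5% |
| 80 / 60 | 66.7, 26.1, 18.2% | 75.0, 94.4, 96.4% |
| 60 / 80 | 75.0, 34.6, 25.0% | 66.7, 91.9, 94.7% |
| 90 / 90 | 90.0, 61.4, 50.0% | 90.0, 98.1, 98.8% |

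**Step 5: accuracy.** In the table, accuracy = (60·Se + 60·Sp)/120 = (Se + Sp)/2. In a population it is Se·p + Sp(1-p). The two agree when Se = Sp. At an assumed 80/60, 70% becomes 63% at 15% and 62% at 10%; at 60/80, 70% becomes 77% and 78%.

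**Step 6: what does not move.** Se and Sp are each computed within one group. Youden's index, LR+, LR-, the diagnostic odds ratio and the ROC curve are built from them, so none depends on the 60:60 ratio.

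**The case against.** The formulas are textbook definitions and correct as descriptions of any 2×2 table. The stated aim is a relationship and a correlation; the plan sets no diagnostic objective, and enuresis is established by observed bedwetting rather than by a blood test. No PPV is reported yet, and no decision in the plan turns on one. All of this stands, and it makes the point minor. It does not remove the point: predictive values are listed among the outputs, and following the stated rule gives figures that apply at 50% prevalence only.

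The target is unnamed, and the objection that enuresis is only inferred is fair. Nocturnal polyuria is assessed in both groups, and vitamin D deficiency has a cut-off of 20 ng/ml. If either were the target, its frequency in the table would not be fixed at 50% and the factors above would not apply, although the sample would still be enriched 1:1 for enuresis. Enuresis remains the natural reading because the title and the sampling are built on it.

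Three stronger readings are tempting, and the documents support none of them:

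- A reader might infer that the whole diagnostic analysis, or the comparison of vitamin D between groups, is compromised. It is not: the quantities in Step 6, the t-test and the chi-square test do not use the sampling ratio as a prevalence.
- A reader might infer that accuracy should be struck out. At 1:1 it is the average of Se and Sp, a legitimate summary linked directly to Youden's index. It needs only a label.
- A reader might compare confidence intervals for the raw and adjusted PPV to ask whether the gap is noise. That comparison is not informative, because both are fixed transformations of the same Se and Sp. The shift in odds is certain once p is given.

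**Conclusion.** The point holds conditionally and is minor. If enuresis is the target and all 120 children enter the table, the planned PPV and NPV are exactly the values at 50% prevalence, and nothing in the plan tells the reader so.

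The 5.7-fold and 9-fold factors illustrate the scale; they should not be read as the error in this study. The 15% and 10% behind them describe all nocturnal enuresis in the general population. The documents give no prevalence for untreated primary monosymptomatic enuresis at three or more nights a week, or for the hospital's referral population. At the assumed 30% the factor is 2.3. The effect on PPV and NPV themselves also depends on Se and Sp, which are assumed throughout.

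**What to change.** In the Statistical methods section:

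1. Name the target condition and the index variable for the ROC and diagnostic analysis.
2. Report Se, Sp, LR+ and LR- with 95% CIs as the main diagnostic results.
3. Omit the raw PPV and NPV, or label them as specific to the 1:1 sample. Label accuracy as the average of Se and Sp.
4. If predictive values are wanted, compute them by Bayes' rule over a stated prevalence range that includes 10%, 15% and higher referral values. Note that Se and Sp come from selected cases and healthy controls and may not carry over to other children, including bedwetters who count towards the 10-15% but belong to neither study group.

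The cost is a few lines of wording and a recalculation from the same table, with no new data. The downside is that a PPV computed at a prevalence below 50% will look less favourable than the raw one.
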